2. STUDY DESIGN

[figure not shown]
This study is a Phase 2, multicenter, randomized, double-masked, dose-ranging, vehicle-controlled, parallel-group clinical trial. Subjects 18 years of age and older with a diagnosis of dry eye disease and experiencing an episodic flare up who meet all study entry criteria will be enrolled. The investigator and his/her staff will not know which study medication the subject is receiving but will be able to determine this in the event of an emergency.

Prior to enrollment, the study will be discussed with prospective subjects and those wishing to enter will be asked to give written informed consent. Informed consent will be obtained prior to any study related procedures being performed. Once informed consent has been obtained, the subjects will be questioned regarding their medical history to determine whether or not they are in satisfactory health to enter the study and to determine if they meet the specific entry criteria.

There will be a total of 7 study visits:

Screening Visit 1 (Day -14 to Day 0), Baseline/Randomization Visit 2 (Day 1), Visit 3 (Day 8), End of Treatment Visit 4 (Day 15), Visit 5 (Day 28), Visit 6 (Day 49) and Study Completion/Early Discontinuation Visit 7 (Day 70).

Study Visit Schematic

*Subjects who discontinue the study during the dosing period (Day 1 through Day 14) will be asked if they would be willing to return to the study site two weeks (\pm 2 days) from the last dose of study drug for the Visit 7/Early Discontinuation Visit, for subject safety. If the subject is willing to return in two weeks for the Visit 7/Early Discontinuation Visit, the subject will be discontinued from the study following the completion of the Visit 7/Early Discontinuation Visit. If the subject is not willing to return in two weeks for the Visit 7/Early Discontinuation Visit, the subject will be discontinued from the study at the current visit and all Visit 7/Early Discontinuation assessments will be performed during the current visit.

Screening (Day -14 to Day 0), Randomization (Day 1), and Dosing Phase (Day 1 to Day 14):

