During the screening phase of the study, subjects who meet all inclusion and none of the exclusion criteria will be randomized in a 1:1:1 ratio: 40 subjects in the 0.02% BSP group, 40 subjects in the 0.04% BSP group, and 40 subjects in the vehicle group. During the dosing phase (Day 1 to Day 14), subjects will instill study drug BID for 14 days. Subjects will receive instructions for dosing at home and for completing a Study Drug Dosing Diary with Drop Comfort Questionnaire during the study dosing phase (Day 1 to Day 14). Subjects (or their caregivers) will be instructed to store the study drug at room temperature (15°- 25°C; 59° - 77°F), to protect the study drug from light and to not freeze the study drug, as well as to instill 2 doses (preferably 8-12 hours apart) every day for 14 days in the study eye and the fellow eye, if applicable. The fellow eye can only be dosed if it was determined by the investigator at baseline that the fellow eye requires relief of dry eye symptoms as well. The fellow eye must follow the same dosing regimen as the study eye.

Visit 3 (Day 8)

Subjects will be assessed for safety and efficacy assessments.

Visit 4 (Day 15): Improvement

Subjects who achieve a 1 unit or better improvement in University of North Carolina (UNC) Dry Eye Management Scale (DEMS) score and a 0.5 point or better improvement in conjunctival hyperemia at Visit 4 (Day 15) when compared to their baseline scores will then be followed for 8 weeks during the evaluation phase (Day 15 to Day 70) to assess for a rebound and safety.

Rebound Assessments at Visit 5 (Day 28), Visit 6 (Day 49), and Visit 7 (Day 70)

Rebound is assessed at Visit 5 (Day 28), Visit 6 (Day 49) and Visit 7 (Day 70) when compared to Visit 4 (Day 15) as a 1 unit or more worsening in UNC DEMS score and a 0.5 point or more worsening in conjunctival hyperemia. Subjects who meet this definition of having a rebound will complete the current visit (either Visit 5 [Day 28], Visit 6 [Day 49] or Visit 7 [Day 70]) and then be discontinued from the study prior to receiving another possible treatment.

Subjects will be instructed to bring all their study drug (used and unused) and subject diaries with them to Visit 3 (Day 8) for review with site staff, and to return their study drug (used and unused) and subject diaries at Visit 4 (Day 15).

Visit 4 (Day 15): No Improvement - Early Discontinuation

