Subjects who do not achieve a 1 unit or better improvement in UNC DEMS score and a 0.5 point or better improvement in conjunctival hyperemia at Visit 4 (Day 15) when compared to their baseline score will complete the Early Discontinuation Visit (Visit 7).

Subjects' safety will be evaluated throughout the study. The safety parameters to be assessed are the incidence, severity, and relationship of adverse events (AEs) and serious adverse events (SAEs), discontinuations due to AEs, changes in visual acuity (VA) and intraocular pressure (IOP), and biomicroscopic and ophthalmoscopic findings in treated eyes.

Efficacy will be assessed as follows: All analyses will be done descriptively. No confirmatory statistical testing will be performed, but exploratory statistical tests may be used to evaluate the efficacy parameters. Data for the study eye will be used for all efficacy analyses.

Primary Efficacy Analysis:

The primary efficacy analysis planned is listed below. Each active treatment group (0.02% and 0.04% BSP) will be independently compared to the Vehicle group. As this is a Phase 2 study, no superiority claims are being tested; therefore, no adjustments will be made for multiple comparisons. Comparisons will be made with a two-sided Fisher's exact test with an alpha-level of 0.05.

1. The proportion of subjects with clinically significant improvement from baseline in UNC DEMS score at Visit 3 (Day 8) will be summarized for each treatment group. A clinically significant improvement is defined as a minimum reduction in UNC DEMS score of 1 unit or more. Subjects who receive another therapeutic treatment for the signs and symptoms of their episodic flare up due to a lack of efficacy at or prior to Visit 3 (Day 8) will be treated as failures.

Secondary Efficacy Analyses:

The two secondary efficacy analyses planned are listed below.

1. The proportion of subjects with clinically significant improvement from baseline in UNC DEMS score at Visit 4 (Day 15) will be summarized for each treatment group. A clinically significant improvement is defined as a minimum reduction in UNC DEMS score of 1 unit or more. Subjects who receive another therapeutic treatment for the signs and symptoms of their episodic flare up due to a lack of efficacy at or prior to Visit 4 (Day 15) will be treated as failures.

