All data summaries and data listings will use the nominal visit names as captured in the eCRF and as per the protocol schedule of visits. Derived visit windows will not be used for the data analysis. For all ‘by visit’ summary analyses of efficacy and safety endpoints, if a subject has an early discontinuation before Visit 6/Day 84, the data from the early discontinuation visit will be included in Visit 6/Day 84 assessment. If a subject has an early discontinuation after Visit 6/Day 84 but before Visit 7/Day 98, the data from the early discontinuation visit will be included in Visit 7/Day 98 assessment.

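### The early-discontinuation rule in Section 10.5 uses visit days that contradict the schedule and, even read by visit number, puts earlier exit data in the Visit 6 rows

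*Combined protocol and SAP*

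**What the plan says.** Section 2 (Study Design) sets the late schedule as "Visit 5 (Day 28), Visit 6 (Day 49) and Study Completion/Early Discontinuation Visit 7 (Day 70". Its rebound paragraph repeats those days.

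Section 10.5 (General Considerations) says that summaries and listings "will use the nominal visit names as captured in the eCRF and as per the protocol schedule of visits" and that no derived windows are used. It then gives a rule for all by-visit efficacy and safety summaries. For an exit before Visit 6, "the data from the early discontinuation visit will be included in Visit 6/Day 84 assessment". The second branch begins "If a subject has an early discontinuation after Visit 6/Day 84 but before Visit 7/Day 98" and sends those data to Visit 7.

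Section 2 builds in exits well before Visit 6:

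- Subjects who fail the joint Day 15 criterion (UNC DEMS and hyperemia) come under the heading "Visit 4 (Day 15): No Improvement - Early Discontinuation". The text says that those who do not improve "when compared to their baseline score will complete the Early Discontinuation Visit (Visit 7").
- Subjects who stop during dosing are asked to return two weeks (within 2 days) "from the last dose of study drug for the Visit 7/Early Discontinuation Visit, for subject safety". If they decline, "all Visit 7/Early Discontinuation assessments will be performed during the current visit".

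**The concern.** There are two faults, and correcting the first leaves the second.

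**Labels.** The rule gives Visits 6 and 7 days that the schedule does not contain. A programmer who applied the printed days would file exits differently from one who applied the visit numbers.

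**Routing.** Under either reading, an assessment made at an exit around Day 15 is shown as a Visit 6 result. The Visit 6 row should describe subjects who improved and have been off drug for several weeks. It would also hold readings taken during or soon after dosing from subjects who did not improve or who dropped out. Leaving at Day 15 is decided by an efficacy outcome, so if the drug works the mix will differ between active and vehicle arms.

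IOP is the plainest example. It is a named safety variable (Section 10.2), is measured from Visit 3 through Visit 7 (Section 8), and its elevation is a listed corticosteroid risk (Section 6). A difference between arms in a Visit 6 IOP row could reflect when the readings were taken rather than what happened after dosing. The summary tables would not show this, because Section 10.6 confines calculated study day to the listings.

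**Working it through.** **1. Labels against the schedule** (Sections 2 and 10.5)

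- Visit 6: 84 − 49 = 35 days apart.
- Visit 7: 98 − 70 = 28 days apart. The two gaps are unequal, so a different day origin cannot explain them.
- 84 − 70 = 14, so the printed Visit 6 day falls two weeks after the last scheduled visit.

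**2. The two readings of the rule**

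| Exit day | By printed day | By visit number |
|---|---|---|
| 8, 15 or 28 | Visit 6 | Visit 6 |
| 60 | Visit 6 | Visit 7 |

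By printed day, every exit up to Day 70 precedes Day 84, so all go to Visit 6 and the second branch is never used. By visit number, the second branch works, but every exit before Day 49 still goes to Visit 6.

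**3. How far the carried data are from Day 49** (exit days from Section 2)

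| Exit | Actual day | Days before Day 49 |
|---|---|---|
| Non-improver, if the exit is on Day 15 | 15 | 49 − 15 = 34 |
| Dropout who returns, earliest | 1 + 14 − 2 = 13 | 49 − 13 = 36 |
| Dropout who returns, latest | 14 + 14 + 2 = 30 | 49 − 30 = 19 |
| Dropout who exits at the current visit, e.g. Day 8 | 8 | 49 − 8 = 41 |

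A subject genuinely seen on Day 49 after a last dose on Day 14 is 49 − 14 = 35 days off drug. A non-improver seen on Day 15 is 1 day off drug, and a returning dropout 12 to 16 days.

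Subjects who rebound at Day 28 complete Visit 5, so their data can stand under Visit 5. The text does not say whether they also count as early-discontinuation visits, so they are left out here.

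**4. Illustration of the mix.** The documents give no exit rates, so *q*, the share of an arm that exits on Day 15, is assumed. Also assumed are 40 subjects per arm (Section 2), one exit record per non-improver, and all improvers attending on Day 49.

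- Exit records in the Visit 6 row = 40*q*. Their share of the row = *q*.
- Mean actual study day of the row = 15*q* + 49(1 − *q*) = 49 − 34*q*.

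| *q* | Exit records of 40 | Mean actual day |
|---|---|---|
| 20% | 8 | 42.2 |
| 30% | 12 | 38.8 |
| 60% | 24 | 28.6 |

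With 30% in one arm and 60% in another, two rows both labelled Visit 6 would differ by 38.8 − 28.6 = 10.2 days in mean timing. With equal rates the mix would not differ by arm, but the mis-dated share would still equal *q*.

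**The case against.** The best case against the point is that little depends on it. The trial is a descriptive Phase 2 study. The primary and secondary endpoints are read at Visits 3 and 4, and no test is specified at Visit 6 or 7. A study-eye IOP rise of 10 mmHg is recorded as an AE and a value of 30 mmHg or more as an SAE (Section 9), so such readings reach the AE tables whichever row they occupy. The listings carry dates and study days. The supplied text shows no specific Visit 6 table for IOP or efficacy; only the general by-visit wording of Section 10.5 supports one. The day of the non-improvers' exit visit is suggested by a heading, and the visit schematic is not available in the supplied text. All of this stands. It limits the consequence but does not remove the mis-dating.

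Four stronger readings are tempting, and the documents do not support them:

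- *The second branch can never operate.* This is true only if the printed days govern. The nominal-visit sentence and the absence of derived windows favour reading by visit number.
- *The carry contradicts the nominal-visit sentence.* A general rule followed by a specific exception is a natural reading, and the eCRF name of the exit visit is not in the supplied text.
- *The primary or secondary results are biased.* The rule moves nothing into Visit 3 or Visit 4. A narrower question is open. If an exit done at Visit 3 or 4 is recorded only as an early-discontinuation visit, the rule would move it to Visit 6 and the observed-data responder denominators could lose it. The text does not say either way.
- *A majority of the Visit 6 row is mis-dated.* That needs an exit rate that the documents do not give.

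**Conclusion.** The rule is wrong as written. Its labels differ from the schedule by 35 and 28 days. Read by visit number, it still shows exit data under Visit 6 that were collected 34 days early (Day 15 non-improvers, if they exit that day), 19 to 36 days early (returning dropouts) or 41 days early (a Day 8 exit). Because the Day 15 exit depends on response, the resulting mix can differ by arm. The shares of 20% to 60% and the mean days are illustrations on assumed rates, and no shift in IOP or any other outcome has been estimated.

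The harm is confined to descriptive by-visit rows, on the condition that data from an exit at Visit 3 or 4 stay under that visit. Per-subject rebound status and the AE tables are unaffected. The point should be fixed before unmasking, but it does not threaten the planned endpoint comparisons if that condition is met.

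**What to change.** Before unmasking:

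1. Reconcile the visit days in Section 10.5 with the schedule in Section 2.
2. Delete the carry of early-discontinuation data into Visit 6 and Visit 7.
3. Keep exit assessments made at a scheduled visit under that visit, with one record per subject per visit. If a scheduled-visit record and an exit record both exist, use the scheduled-visit record. This also settles the open question about exits at Visits 3 and 4.
4. Report all other exit assessments in a separate Early Discontinuation row, with actual study day summarized by arm.

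The cost is SAP wording and table shells. No patient procedure, visit or data collection changes.

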10.6. General Derived and Transformed Data

Age, in completed years, at informed consent date will be defined as: Age (years) = integer value (Date of Informed Consent – Date of Birth + 1) / 365.25).

Study day will be calculated using the first dosing date as the reference date. If the date of interest occurs on or after the first dosing date, then study day will be calculated as (date of interest – date of first dosing) + 1. If the date of interest occurs prior to the first dosing date, then study day will be calculated as (date of interest – date of first dosing). The day of the first dosing will be identified as Study Day 1 according to Clinical Data Interchange Standards Consortium (CDISC) standard. If a subject is dosed but dosing dates are missing, then the randomization date will be used as the first dosing date for the calculation of study day. Data listings will present study days in addition

to assessment dates, where applicable. As per above, all data summaries and data listings will use the nominal visit names as captured in the CRF and as per the protocol schedule of visits. The calculated study day as per CDISC will only be used in data listings to indicate the distance of an event from the dosing day.

Baseline will be defined as the last available, non-missing observation prior to the first dosing time with study drug, unless specifically mentioned otherwise. When baseline is derived, all data before the first dosing with study drug, including unscheduled visits before the first dosing with study drug, will be used for the derivation of baseline value.

Change from Baseline: Assessment value at post-dosing visit – baseline value. It should be noted that if the derived baseline as above is missing for one parameter, then the change from baseline will not be available for this parameter. Imputation of baseline data will not be conducted.

Percentage Change from Baseline:

$$(\text{Assessment value at post-dosing visit} - \text{baseline value}) * 100 / \text{baseline value}$$

11. EFFICACY

11.1. Primary and Secondary Efficacy Analysis: UNC DEMS Reduction

UNC DEMS is used to measure the primary and one of the secondary endpoints. UNC DEMS score is rated from 1 to 10, with a higher score associated more severe dry eye symptoms. Data are NOT collected separately for study/fellow eyes. UNC DEMS is assessed at each study visit.

The primary endpoint is the proportion of subjects with clinically significant improvement from baseline in UNC DEMS score at Visit 3 (Day 8). A clinically significant improvement is defined as a minimum reduction in UNC DEMS score of 1 unit or more. Subjects who receive another therapeutic treatment for the signs and symptoms of their episodic flare up due to a lack of efficacy at or prior to Visit 3 (Day 8) will be treated as failures.

One of the secondary endpoints is the proportion of subjects with clinically significant improvement from baseline in UNC DEMS score at Visit 4 (Day 15). A clinically significant improvement is defined as a minimum reduction in UNC DEMS score of 1 unit or more. Subjects who receive another therapeutic treatment for the signs and symptoms of their episodic flare up due to a lack of efficacy at or prior to Visit 4 (Day 15) will be treated as failures.

Responder Analysis

Subjects with 1 unit or more reduction in UNC DEMS score from baseline are defined as responders, and response rates will be summarized at Visit 3 (Day 8) and Visit 4 (Day 15). All other subjects with non-missing data will be treated as non-responders. Further, subjects who receive another therapeutic treatment for the signs and symptoms of their episodic flare up due to a lack of efficacy at or prior to Visit 3 (Day 8)/Visit 4 (Day 15) will be treated as failures. It should be noted that subjects will be treated as non-responders from the time point that they received non-study treatment for the signs and symptoms of their episodic flare up due to a lack of efficacy.

For the ITT responder analysis, the analysis will be conducted based on the observed available

data without any imputation for missing data.

The responder rate will be summarized at Visit 3 (Day 8) and Visit 4 (Day 15) by treatment group, along with its 95% CI which will be estimated by Clopper-Pearson exact method. The difference in responder rates between each of the SURF- 200 formulations and vehicle at each visit will be compared by Fisher's exact method.

11.2. Secondary Endpoint: Conjunctival Hyperemia Grade Reduction

Conjunctival hyperemia grade is used to measure one of the secondary endpoints, and will be assessed using a consistent light source, examiner and exam room from visit to visit. Conjunctival hyperemia is graded from 0 to 3, with a higher grade (score) associated more severe conditions. Data are collected separately for study/fellow eyes. Conjunctival hyperemia is assessed at each study visit.

The proportion of subjects with clinically significant improvement from baseline in conjunctival hyperemia in the study eyes at Visit 3 (Day 8) will be summarized for each treatment group. A clinically significant improvement is defined as a reduction of 0.5 points or more. Subjects who receive another therapeutic treatment for the signs and symptoms of their episodic flare up due to a lack of efficacy at or prior to Visit 3 (Day 8) will be treated as failures.

Responder Analysis

Subjects with 0.5 point or more reduction in conjunctival hyperemia grade (score) from baseline are defined as responders, and responder rates will be summarized at Visit 3 (Day 8). All other subjects with non-missing data will be treated as non-responders. Further, subjects who receive another therapeutic treatment for the signs and symptoms of their episodic flare up due to a lack of efficacy at or prior to Visit 3 (Day 8) will be treated as failures. It should be noted that subjects will be treated as non-responders from the time point once they received non-study treatment for the signs and symptoms of their episodic flare up due to a lack of efficacy.

For the ITT responder analysis, the first analysis will be conducted based on the observed available data without any imputation for missing data.

The same responder analysis as conducted for the primary endpoint will be conducted for conjunctival hyperemia response analysis. That is, for each treatment group, the responder rates and their Clopper-Pearson exact 95% CIs will be estimated at Visit 3 (Day 8). The responder rate difference and its 95% CI between each of the SURF-200 formulations (0.02% and 0.04% BSP) vs vehicle at Visit 3 (Day 8) will be estimated as well. The difference in responder rates between each of the SURF-200 formulations and vehicle at each visit will be compared by Fisher's exact method.

The responder analysis for conjunctival hyperemia grade is only applicable to study eye data.

12. SAFETY

12.1. Adverse Events

Adverse events will be summarized separately for those occurring in the study eye, in the fellow eye, and non-ocular events. For overall AE incidence summary, one table for ocular AEs (study eye and fellow eye combined) will be reported. In this table, each subject will be counted only once in each summary category, to avoid correlated data. However, the results should be interpreted with caution because fellow eyes are selective samples by study design. Regardless of whether the fellow eye is treated or not, all AEs reported for the fellow eye will be included for the safety analysis. AEs marked as 'Both Eyes (OU)' from the AE CRF page will be summarized both for study eye and fellow eye.

All AE verbatim terms will be coded using Medical Dictionary for Regulatory Activities (MedDRA) version 23.0 Update. Terms will be coded to the full MedDRA hierarchy, but the system organ class (SOC) and preferred term (PT) will be of primary interest for the analysis.

Treatment emergent adverse events (TEAEs) are defined as AEs that first occurred or worsened on or after the date of first administration of study drug. If missing dates or time prevent a clear determination as to whether the AE is treatment emergent, the AE will be regarded as a TEAE.

While all AEs will be summarized, the main AE summaries will be restricted to TEAEs only. Treatment emergent adverse events will be summarized descriptively. For the summary of TEAEs, if a subject experienced the same AE multiple times, this will only be counted once for the purpose of counting the number of patients experiencing that AE. Summary tables will include the number of subjects (%) experiencing an AE and the number of AEs.

The TEAE summaries will include:

- Overall Summary of Subjects with at Least One Adverse Event
- Summary of TEAEs by SOC and PT
- Summary of TEAEs with an Incidence $\geq 5\%$ by SOC and PT
- Summary of Serious TEAEs by SOC and PT

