8. CLINICAL ASSESSMENTS/EXAMINATION PROCEDURES

Assessments Completed by Subjects:

UNC DEMS Questionnaire: The UNC DEMS will be completed by subjects at Visit 1 (Screening; Day -14 to Day 0) and only at Visit 2 (Day 1, prior to randomization) if Visit 2 is >5 days following Visit 1. The UNC DEMS will also be completed by subjects at Visit 3 (Day 8) through Study Completion/Early Discontinuation Visit 7 (Day 70).

Dosing Diary with Drop Comfort Questionnaire: Subjects will be given a Dosing Diary with Drop Comfort Questionnaire to record study drug dose instillation dates and times for each dose, as well as to record their responses to the Drop Comfort Questionnaire twice weekly during the dosing period (Day 1 to Day 14).

Assessments Completed by Investigators:

Best-Corrected Visual Acuity (BCVA): BCVA will be performed in both eyes at Visit 1 (Screening; Day -14 to Day 0) and only at Visit 2 (Day 1, prior to randomization) if Visit 2 is >5 days following Visit 1. BCVA will also be performed in treated eyes at Visit 3 (Day 8) through Study Completion/Early Discontinuation Visit 7 (Day 70). Log of the minimum angle of resolution (logMAR) score using ETDRS (Early Treatment Diabetic Retinopathy Study) chart will be used to measure BCVA. Performing a pinhole test is allowed as long as its use remains consistent for the same subject throughout all study visits.

Biomicroscopy: Slit lamp biomicroscopy will be performed to observe the overall health of the eye, including the lid/lashes, conjunctiva, cornea, anterior chamber, iris, and lens. This will be performed in both eyes at Visit 1 (Screening; Day -14 to Day 0) and only at Visit 2 (Day 1) if Visit 2 is >5 days following Visit 1. Slit lamp biomicroscopy will also be performed in treated eyes at Visit 3 (Day 8) through Study Completion/Early Discontinuation Visit 7 (Day 70).

Ophthalmoscopy: An ophthalmoscopy examination will be performed in both eyes at Screening Visit 1 (Day -14 to Day 0) and in treated eyes at End of Treatment Visit 4 (Day 15). If anesthesia is used to perform the ophthalmoscopy examination, symptom assessments will be completed first before anesthesia administration or dilation.

Intraocular Pressure (IOP): IOP will be measured in both eyes at Visit 1 (Screening; Day -14 to Day 0) and only at Visit 2 (Day 1) if Visit 2 is >5 days following Visit 1. IOP will also be measured in treated eyes at Visit 3 (Day 8) through Study Completion/Early Discontinuation Visit 7 (Day 70).

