10.3. Analysis Populations

Intent-to-Treat Population: The Intent-to-Treat (ITT) population includes all randomized subjects regardless of whether post-baseline measures are collected, or study drug is received. Subjects in the ITT population will be analyzed in the treatment group to which they were assigned by the randomization schedule, regardless of which study drug they receive.

Per Protocol Population: The per-protocol (PP) population includes all subjects who received at least one dose of study drug and had no significant protocol deviations.

Safety Population: The safety population includes all subjects who receive at least 1 dose of the study drug. Subjects in the safety population will be analyzed in the treatment group for the study drug they received.

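### The fellow-eye adverse event summary mixes dosed fellow eyes with undosed ones that have no scheduled post-baseline examination, so its percentage describes neither group

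*Combined protocol and SAP*

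**What the plan says.** - **Who is dosed.** Section 2 has drug instilled "in the study eye and the fellow eye, if applicable". It adds the condition: "The fellow eye can only be dosed if it was determined by the investigator at baseline that the fellow eye requires relief". Dosed and undosed fellow eyes can therefore both occur within an arm.
- **Who is examined.** Section 8 examines both eyes at screening, and most tests are repeated before dosing at Visit 2 if that visit falls more than 5 days later. After that the schedule narrows: "IOP will also be measured in treated eyes at Visit 3 (Day 8) through Study Completion/Early Discontinuation Visit 7 (Day 70", and likewise "Slit lamp biomicroscopy will also be performed in treated eyes at Visit 3 (Day 8". Visual acuity, ophthalmoscopy (Visit 4), hyperemia, tear break-up time, staining and Schirmer follow the same treated-eye rule.
- **How AEs are tabulated.** Section 12.1: "Adverse events will be summarized separately for those occurring in the study eye, in the fellow eye, and non-ocular events". The inclusion rule is "Regardless of whether the fellow eye is treated or not, all AEs reported for the fellow eye will be included for the safety analysis". A combined ocular table counts each subject once per category and carries a caution that fellow eyes are a selected sample.
- **What is treatment-emergent.** Section 12.1 dates this from first study drug administration. It does not require that the affected eye was dosed.
- **Denominator.** Section 12.1 states none. Section 10.5 defaults to the number of patients in the relevant population, and Section 10.3 defines that by subject: "The safety population includes all subjects who receive at least 1 dose of the study drug".

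**The concern.** A fellow-eye percentage with all dosed subjects beneath it mixes two kinds of eye. Dosed fellow eyes are exposed and examined on schedule. Undosed fellow eyes are unexposed, were judged at baseline not to need treatment, and are not examined on schedule afterwards. An event that is found only at the slit lamp or on ophthalmoscopy can hardly appear in the second group, yet that group still sits in the denominator.

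Safety and tolerability are part of the study objective. With 40 subjects planned per arm, dosed fellow eyes are the only ocular exposure data beyond the study eye. A reader of the planned table could not recover the dosed-eye rate, because the plan does not call for the number of dosed fellow eyes. An event after Day 1 in an eye that never received drug would also be reported as treatment-emergent in that arm, with nothing in the table to show it.

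**Working it through.** The documents give no fellow-eye dosing share, AE rate or related calculation, so there is no planned figure to reproduce. The text fixes the mechanism, and the size can only be illustrated.

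**Which events are affected.** Section 9 decides this.

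- Treatment-emergent slit-lamp findings, and new or significantly worse ophthalmoscopy findings, are to be recorded as AEs. Neither rule is limited to the study eye, and both depend on an examination that undosed fellow eyes do not routinely get. These are the main affected events.
- The rule that an IOP of 30 mmHg or higher is a serious AE also names no eye.
- The 10 mmHg IOP-rise and 3-line visual acuity triggers name the study eye only. A dosed fellow eye has no mandated AE under them, and splitting the table would not create one.

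**Dilution of the fellow-eye percentage.** Let f be the share of fellow eyes dosed, d the AE rate in dosed fellow eyes and u the reported rate in undosed ones. With all subjects as denominator:

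reported rate = f × d + (1 − f) × u

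Assume d = 10%, with u = 0% or 1%:

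| f | u = 0% | u = 1% |
|---|---|---|
| 0.5 | 0.5 × 10 = 5.0% | 5.0 + 0.5 × 1 = 5.5% |
| 0.7 | 0.7 × 10 = 7.0% | 7.0 + 0.3 × 1 = 7.3% |
| 0.9 | 0.9 × 10 = 9.0% | 9.0 + 0.1 × 1 = 9.1% |
| 1.0 | 10.0% | 10.0% |

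With u = 2% the result is 6.0% at f = 0.5 and 9.2% at f = 0.9. If u = d there is no dilution at any f. With dosed fellow eyes as denominator, the rate is 10% in every row.

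**Arm differences.** Assume 20% on active and 5% on vehicle in dosed fellow eyes, u = 0, and the same f in both arms. The true difference of 15 points is reported as 0.75 × 15 = 11.25 points at f = 0.75 and 0.5 × 15 = 7.5 points at f = 0.5.

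**Small counts.** With 40 per arm and 20 fellow eyes dosed, one event is 1/20 = 5.0% of dosed eyes but 1/40 = 2.5% of subjects. If the plan's 5% incidence table is cut per arm and per eye, that event drops out.

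**Power.** In the 20% versus 5% example at f = 0.5, normal-approximation power at two-sided 0.05 is 28.1% pooled (n = 40 per arm) and 29.5% for dosed eyes alone (n = 20 per arm). What suffers is the reported rate and difference, not power.

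**Combined ocular table.** Each subject counts once per category, and the study eye is always a dosing target, so the denominator consists of exposed subjects. Undosed fellow eyes cannot dilute it. They can only add events.

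**The case against.** Several points against this stand.

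- **Convention.** Counting every AE and judging treatment emergence by subject are common practice. The gap is the missing split and denominator, not the inclusion.
- **Ascertainment is not nil.** A reader might infer that an undosed fellow eye can yield an AE only by spontaneous report. The documents do not support that. Subjects are queried at every visit (Section 8), events elicited by questioning must be recorded, and additional examinations are allowed (Section 9).
- **IOP rise is a poor example.** A reader might infer that pooling hides IOP rises in dosed fellow eyes. The 10 mmHg trigger applies to the study eye only, so that loss comes mostly from the trigger, not from the table.
- **Chance imbalance in dosing is a weak argument.** At a 10% rate in dosed eyes, shares of 50% and 70% would create a gap of 7.0 − 5.0 = 2.0 points, less than one subject in 40 (2.5 points). At a common 60% share, the standard error of the between-arm gap in share is √(2 × 0.6 × 0.4 / 40) ≈ 11 points, so a 20-point gap is about 1.8 standard errors.
- **Undosed eyes are not a clean unexposed reference.** They were selected as not needing treatment and are not examined on schedule.
- **Partial safeguards exist.** The study-eye table is separate, relationship to study drug is assessed, all data are listed, and the study is descriptive.

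Two limits concern the text itself. Section 10.5 also refers to percentages of available data, so the denominator is an inference. The available text stops within the list of treatment-emergent AE summaries, so a later table by dosing status cannot be ruled out.

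None of this makes the fellow-eye percentage interpretable. The caution in Section 12.1 acknowledges selection but supplies neither a split nor a count of dosed fellow eyes.

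**Conclusion.** The point holds for the fellow-eye summary, as a minor-to-moderate reporting weakness. If the Section 10.5 default denominator applies and some fellow eyes are undosed, the fellow-eye percentage estimates neither the exposed nor the unexposed rate. The likely direction is to understate examination-detected AEs in dosed fellow eyes, because the undosed eyes are both unexposed and less closely observed.

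The size cannot be derived from the documents. It depends wholly on the assumed rates and the unknown dosed share, and ranges from nothing (all fellow eyes dosed, or equal rates) to about half (half dosed, almost no events in undosed eyes).

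A reader might extend the dilution claim to the combined ocular table or to the trial's ocular safety results as a whole. The documents do not support that. In the combined table the only issue is that events in never-dosed eyes count as treatment-emergent, and the study-eye summary is untouched.

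**What to change.** In Section 12.1:

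1. Report the number of dosed fellow eyes in each arm.
2. Present fellow-eye treatment-emergent AEs separately for dosed and undosed fellow eyes. The denominators are the subjects whose fellow eye received at least one dose, and the remaining subjects in the safety population. State both explicitly so that the Section 10.5 default does not apply.
3. Keep every AE in the combined ocular table and the listings, and flag those in undosed eyes. Removing them from the main row of the combined table is not needed.

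The cost is SAP wording and one extra table split, with smaller denominators in each part. No new examinations are required. The documents do not say that the diary records doses by eye. Sites must nevertheless know which fellow eyes are treated in order to follow the Section 8 schedule, so the sponsor should confirm that this status is held in the database for each subject.
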